## [name] 2020 PROJECT OUTLINE: IRB #8242

### INTRODUCTION

Global hypertension rates have reached epidemic proportions with upwards of one billion individuals diagnosed and estimates that 1/3 of the global adult population is hypertensive. Blood pressure (BP) is a primary risk factor for cardiovascular disease. There are over a million firefighters in America, and firefighting is one of the most hazardous and dangerous jobs with an inherent increased risk of death, just by nature of the work. In fact, many firefighters have hypertension, and cardiac-related incidents are the leading cause of death among firefighters. Also, BP control remains an issue in firefighters, with close to 74% of hypertensive firefighters not having adequate control of their BP. Research that examines BP in firefighters is scarce, and quantifying the BP surge that occurs with pager activation has never been done.

It is known that exercise training improves cardiovascular health, lowers lipid levels, reduces inflammation, and reduces BP. Yet, it is interesting that the National Fire Protection Agency (NFPA) does not require fire companies to have fitness testing or programming for the crew. The NFPA has established that the demands of firefighting require a fitness level of a  $VO_{2\text{max}}$  equivalent of 42 ml/kg/min. Yet, only 20% of volunteer firefighters meet this fitness threshold. And, even worse is that <30% of fire stations have a fitness program or fitness monitoring as part of their standard operating procedures.

It is also known that a healthy diet improves cardiovascular health, lowers lipid levels, reduces inflammation, and reduces BP. Evidence suggests that the Mediterranean diet can improve cardiovascular health, and the Mediterranean diet has been touted the top heart-healthy diet for 2 years in a row. The diet includes a high consumption of fruits and vegetables, a moderate consumption of fish, nuts, low-fat diary, and wine, and a low consumption of red meat and other meat products. Dietary patterns like this reduce inflammation and improve vascular function, which will benefit firefighters. Firefighters know that diet is important, yet they don't know how to modify their diet. Importantly, a recent survey study done at Harvard found that the Mediterranean diet is one that firefighters actually would prefer.

It is not known whether an exercise and diet intervention can reduce the blood pressure surge that occurs when a pager alarm sounds. ABP monitoring is an at home BP monitoring system, which has recently been clinically recommended by guidelines. Normal morning BP surge is established as a physiological event, yet an exaggerated surge is a known cardiovascular risk. Therefore it can be assumed that the BP surge that occurs with pager alarms must also present severe risk. In prior studies, we have found that the BP surge with pager alarm in firefighters can be extreme.

## **RESEARCH PROTOCOL**

This study is a pre-post exercise and diet intervention study with 2 groups: firefighters and civilians. For the study, firefighters will be recruited from local fire departments and civilians will be recruited from the surrounding areas. The only compensation will be for parking while they are on campus for testing appointments. A study description document is attached which will be used to supplement the word-of-mouth advertising done by walking into local firehouses.

The population is seemingly healthy and low-risk, so physician referral or approval is not needed. Criteria for inclusion: adult 18 years of age and older; no history of renal disease, diabetes, or cardiovascular incident requiring surgery; no existing orthopedic issues that preclude exercise; no more than one anti-hypertensive or cholesterol medication.

### Brief protocol summary:

Study participants from both groups (firefighters & civilians) will be enrolled for a total of about 8 weeks. During this time period they will complete the following steps:

#### 1. Orientation and informed consent (15-30 min)

Each participant will provide informed consent and complete a health/exercise history questionnaire. Consent will be obtained in a face-to-face meeting by the principle investigator, [name]. The study will be explained, any questions answered, and then consent will be signed. Each participant will receive a copy of the signed consent form.

#### 2. Diet training (includes a [study](#) manual and a 45-minute training session with study personnel)

Dietary training will be provided. This will include the [study](#) manual (attached to application email) and a 45-minute session where the study participants are taught about the Mediterranean diet and given specific instructions on serving sizes for the food groups.

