#### 3. Pre-intervention testing

- a. Morning fasted study (45 min)
- b. Fitness test session (45 min)
- c. Blood pressure monitoring (includes wearing an ambulatory blood pressure monitor for 12-hours and a 30 min appointment to get set-up on the monitor)

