#### 4. At-home and self-report 6-week intervention (circuit workout 3-times per week and a Mediterranean diet)

Each participant will undergo 6-weeks of intervention (diet and exercise). They will self-report the number of times per week that they complete the circuit workout, and they will self-report the number of servings per food group that they eat while following the diet. The workouts are done at home, in the fire station, or in a fitness center.

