### **Pre-Intervention Testing Visits**

All participants will complete three testing components during pre-intervention. This includes a morning ***fasted study***, a ***blood pressure monitoring***, and a ***fitness test***. We coordinate these appointment times to fit into participant's schedule.

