#### ***Fasted Testing Appointment:***

The total time for this visit will be around 45 minutes. ***This test will occur on UNH campus in NH Hall.*** They will be required to fast for 10 hours before coming into the lab for the testing. For this visit, we ask that they avoid food or drink (water is allowed) for at least 10 hours before coming into the lab. We also ask that they avoid alcohol and exercise the night before. Height, weight, and blood pressure will be taken. Body composition will be measured, glucose and cholesterol levels measured, a blood draw collected, and blood vessel ultrasound and pressure studies will be done.

***Considering that the population is seemingly healthy based on other exclusion criteria, it is still possible to identify high blood pressure or high lipid/glucose levels in the participants. This would not be an exclusion from the study. If this occurs, we inform them and offer to provide them with the data, if they wanted to follow-up with their physician.***

**Body composition test** will tell the investigators what percentage of the body is fat, muscle and bone. The instrument that measures body composition is called bioelectrical impedance (BIA). The machine will cause a very small current to travel through the body for 2-3 seconds, but nothing will be felt. To do this test, they will lie on a table on their back with left foot exposed. To collect the measurements, a technician will place two electrodes on the left foot and two electrodes on left hand.

**Blood glucose and cholesterol measurements** will tell the investigators what the levels of fasted plasma glucose and cholesterol are. We will be measuring these with a finger-prick test. Only one finger prick will occur, and a single large drop of blood will be collected.

**Plasma inflammation, oxidative stress, and vasodilation levels.** A blood draw will occur where we collect 2 tubes of blood (equivalent of 7 tsp or 1.2 oz). This will allow us to measure common markers that circulate in the blood which are related to heart health.

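### The step list puts diet training before the baseline tests, with no request to keep the usual diet in between, so the baseline could be partly treated

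*Combined protocol and SAP*

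**What the plan says.** The Brief protocol summary says that participants "will be enrolled for a total of about 8 weeks" and adds: "During this time period they will complete the following steps". Five numbered items follow.

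- Step 1 is orientation and consent.
- Step 2 is diet training: a manual, plus "a 45-minute session where the study participants are taught about the Mediterranean diet and given specific instructions on serving sizes for the food groups".
- The next item is headed "3. Pre-intervention testing". It covers the fasted study, the fitness test and ambulatory blood pressure monitoring.
- Step 4 is the six-week diet and exercise intervention.
- Step 5 is post-testing, defined by reference back to item 3.

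The detailed sections are laid out differently. They describe the testing visits first and put Pre-Intervention Diet Training later, under the six-week diet component. They do not state which comes first in time.

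The Fasted Testing Appointment section gives two preparatory instructions: "we ask that they avoid food or drink (water is allowed) for at least 10 hours before coming into the lab" and "We also ask that they avoid alcohol and exercise the night before". Usual diet is not mentioned. On scheduling, Pre-Intervention Testing Visits says "We coordinate these appointment times to fit into" the participant's schedule. It sets no limit on the time between training and testing.

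The single 3-day food record is to be made before the diet begins and is used to set serving numbers. Its timing relative to the training session is not given. Weekly serving entry, described under Diet Intervention, runs only while the diet phase is under way.

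**The concern.** Teaching the diet is the first part of delivering it. The Introduction says that firefighters recognise the importance of diet but lack the knowledge to change theirs, and that the Mediterranean diet is one they would favour. Training supplies that knowledge. Some participants may start to eat differently before their baseline is measured.

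This matters because both groups get the intervention and there is no untreated control. For the within-group change, which the DATA section tests with paired t-tests, each participant's own baseline is the only reference. A baseline measured after some dietary change is partly treated, and it cannot be measured again once the intervention has begun. The fasting glucose, cholesterol and blood markers that serve the second aim are exposed in the same way as the blood pressure surge.

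The food record raises a second issue. If it is kept after training, it may not show usual intake, yet it guides the servings prescribed.

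**Working it through.** **Order of events.** The passages compare as follows.

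| Source | What it gives | Does it fix the order? |
|---|---|---|
| Brief protocol summary | Training is step 2, baseline tests step 3, intervention step 4 | Yes, by numbered steps |
| Testing visit sections | Content of each test, placed before the training section | No |
| Pre-Intervention Diet Training | Content of training; food record before the diet starts | No; only record before diet |
| Diet Intervention | Weekly serving entry during the diet phase | No |

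The numbered list is the only stated sequence, and it puts training first. The later layout leaves room for the opposite reading but does not state it.

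**Safeguards in the gap.** Three were looked for.

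1. An instruction to keep the usual diet: none in the available text.
2. Tracking of intake between training and baseline: none.
3. A food record tied to a point before training: no, it is tied only to the start of the diet.

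**Length of the gap.**

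- Enrolment: 8 × 7 = 56 days (approximate).
- Intervention: 6 × 7 = 42 days.
- Remainder: 56 − 42 = 14 days.

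These 14 days or so also have to hold consent, the food record, three baseline tests and all post-testing. The gap from training to a baseline test is therefore at least 0 and less than about 14 days. It may differ between participants because visits are fitted to their schedules.

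**Effect on the within-group change.** Let *a* be the degree of early adoption, *w* the gap in weeks and *r* the diet response per week.

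- No early adoption (*a* = 0): baseline is untreated and the loss is 0.
- Linear response: baseline = *a·w·r*; post = *a·w·r* + 6*r*; change = 6*r*. The loss is 0 for any *a* and *w*.
- Response that levels off: suppose the diet effect reaches the same plateau *D* by post-testing either way, and an amount *b* > 0 is already present at baseline. The observed diet part is *D* − *b*, so the loss is *b*. If diet and exercise effects add, the exercise part *E* is untouched and the total change is (*D* − *b*) + *E*.

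A loss therefore needs both early adoption and a response that levels off. The documents give no input for either, so no percentage can be put on it.

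**Effect on the interaction.** With mean early change *b*₁ in firefighters and *b*₂ in civilians under the plateau case, the group difference in change shifts by *b*₂ − *b*₁. It is 0 when early change is equal in the two groups.

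**The case against.** The strongest reply is that the documents already separate learning the diet from starting it. The diet belongs to the six-week period after testing. Servings depend on a food record, and some are adjusted for body size, while height and weight are taken at the fasted baseline visit. On this reading, step 2 is general teaching and early adoption would be a departure from the schedule. That is a fair account of the intent. It does not prevent participants from acting on general teaching, and the dependence of servings on measurements taken at step 3 is itself a reason to settle the order.

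Second, the study manual and consent pages are the natural places for a usual-diet instruction. Neither was available for this review, and one section of the document had been removed. This stands as a limit: such an instruction may exist there.

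Third, the first two aims compare firefighters with civilians through the condition-by-time interaction, and the paired t-tests are post hoc. This also stands. The interaction is biased only by unequal early change, and nothing in the documents shows that. However, the DATA section also names the effect of the intervention on surge change as an interest, and that effect rests on the within-group comparison.

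Fourth, one sentence asking for usual diet might be enough. It would meet most of the concern, but it would not ensure that the food record precedes training, and departures could not be identified without dates.

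**Conclusion.** The point holds as a possibility that the plan leaves open. It is not a demonstrated bias. The only stated sequence trains participants in the diet before their baseline is measured, and the available text neither asks them to keep their usual diet nor tracks intake in the gap.

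The size is unknown and may be zero. The gap is under about 14 days. Any understatement of the within-group change requires early adoption together with a response that levels off, and the error would then run toward understating benefit. Only the diet part is concerned, since no exercise training is described before baseline.

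The conclusion assumes that the numbered steps are meant as a sequence and that no usual-diet instruction stands in the material not available here. The change is worth making because the exposure cannot be corrected afterwards and prevention is cheap.

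**What to change.** Reconcile the Brief protocol summary with Pre-Intervention Diet Training so that both give the same order:

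1. Complete the 3-day food record and all three baseline tests, in either order, before the diet training session and release of the manual.
2. Ask participants to keep their usual diet until these are done.
3. Record the dates of the food record, each baseline test, the training session and the start of the intervention, so that any participant trained first can be identified and reported.

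The cost is a small scheduling constraint and a few date fields. The protocol already describes training as an appointment, so a separate session may already be planned. If training would otherwise have been held at the consent visit, one extra appointment may be needed; the documents do not say. If testing already comes first in practice, the change only corrects the step list.

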#### 3. Pre-intervention testing

- a. Morning fasted study (45 min)
- b. Fitness test session (45 min)
- c. Blood pressure monitoring (includes wearing an ambulatory blood pressure monitor for 12-hours and a 30 min appointment to get set-up on the monitor)

#### 4. At-home and self-report 6-week intervention (circuit workout 3-times per week and a Mediterranean diet)

Each participant will undergo 6-weeks of intervention (diet and exercise). They will self-report the number of times per week that they complete the circuit workout, and they will self-report the number of servings per food group that they eat while following the diet. The workouts are done at home, in the fire station, or in a fitness center.

#### 5. Post-intervention health and fitness testing which will be the same as pre-testing (#3).

The specifics of each of the appointments are outlined below. During each visit to the lab, to confirm and remind what the study includes, each participant will receive a verbal explanation of the measures collected that day and asked if they have any questions. They will also be asked if they still provide consent.

### **Orientation & Consent**

Study participants will learn about the study, have questions answered and review the consent form. They will complete the wellness questionnaire.

They will also complete a short 21-item scale that asks questions related to their feelings over the past week. One of the main components of blood pressure is emotional response, so for this study we will also assess participants stress and anxiety levels with the Depression, Anxiety, and Stress Scales (DASS-21) scale. The DASS-21 is a 21-item self-reported scale that will determine the presence and severity of the three listed psychometric characteristics above.

The reliabilities of the DASS-21 (internal consistencies) Anxiety, Depression, Stress, and Total scales are 0.88 (95% CI = 0.87-.89) for the Depression scale, 0.82 (95% CI = 0.80-.83) for the Anxiety scale, 0.90 (95% CI = 0.89-.91) for the Stress scale, and 0.93 (95% CI = 0.93-.94) for the Total scale.

The DASS-21 may be administered and scored by non-psychologists, and none of the items refers to suicidal tendencies. The primary function of the DASS-21 is to assess the severity of symptoms of depression, anxiety and stress. Since the scale was developed with non-clinical samples, it is suitable for even adolescents and adults, so can be considered low risk. Despite it being low risk, a comment has been placed in the Risk section of the consent form that states: "The risk associated with completing this short 21-item survey is that you may feel uncomfortable while answering the questions. If you feel this and your symptoms are severe, we will work with you to refer you to a proper clinician who is part of your health network."

### **Pre-Intervention Testing Visits**

All participants will complete three testing components during pre-intervention. This includes a morning ***fasted study***, a ***blood pressure monitoring***, and a ***fitness test***. We coordinate these appointment times to fit into participant's schedule.

#### ***Fasted Testing Appointment:***

The total time for this visit will be around 45 minutes. ***This test will occur on UNH campus in NH Hall.*** They will be required to fast for 10 hours before coming into the lab for the testing. For this visit, we ask that they avoid food or drink (water is allowed) for at least 10 hours before coming into the lab. We also ask that they avoid alcohol and exercise the night before. Height, weight, and blood pressure will be taken. Body composition will be measured, glucose and cholesterol levels measured, a blood draw collected, and blood vessel ultrasound and pressure studies will be done.

***Considering that the population is seemingly healthy based on other exclusion criteria, it is still possible to identify high blood pressure or high lipid/glucose levels in the participants. This would not be an exclusion from the study. If this occurs, we inform them and offer to provide them with the data, if they wanted to follow-up with their physician.***

**Body composition test** will tell the investigators what percentage of the body is fat, muscle and bone. The instrument that measures body composition is called bioelectrical impedance (BIA). The machine will cause a very small current to travel through the body for 2-3 seconds, but nothing will be felt. To do this test, they will lie on a table on their back with left foot exposed. To collect the measurements, a technician will place two electrodes on the left foot and two electrodes on left hand.

**Blood glucose and cholesterol measurements** will tell the investigators what the levels of fasted plasma glucose and cholesterol are. We will be measuring these with a finger-prick test. Only one finger prick will occur, and a single large drop of blood will be collected.

**Plasma inflammation, oxidative stress, and vasodilation levels.** A blood draw will occur where we collect 2 tubes of blood (equivalent of 7 tsp or 1.2 oz). This will allow us to measure common markers that circulate in the blood which are related to heart health.

**Blood vessel ultrasound and pressure measures.** We will be checking the function of blood vessels through the use of several machines. No needles will be used for this test. We will collect images of the carotid artery blood vessel in the neck. Separately, we will also use a large cuff device called a pulse wave analysis system, this will allow us to measure central blood pressure (the actual blood pressure at heart level and not in the arm). This test allows us to see how stiff blood vessels are. For this, we will take some measurements and the cuff will squeeze quickly to get a measurement. We will place a cuff on the arm for measurement and then next place a cuff separately on the leg for a measurement.

#### ***Blood Pressure Monitoring appointment:***

This requires a visit to learn about the ambulatory blood pressure monitor and to get set-up with a cuff and monitor. The total time for this is about 30 minutes. ***This will occur on UNH campus in NH hall.*** The system is an at-home blood pressure monitor that is about the size of a cell phone. It will take measurements every half hour during a 12-hour period. While wearing the cuff and monitor, when the pager goes off, they will push the monitor's button to force an automatic blood pressure reading. We will show you how to do this during the visit to the lab. If they are a firefighter, we also ask that they remove the monitor device right before donning fire gear and take the monitor to the call on the apparatus. We ask them to remove it while wearing your gear because monitors will not record blood pressure when you move. This method is effective and has been done in the lab during our studies. This method has also been done in prior cohorts of this study that were completed at other institutions. Once they get back on the apparatus to return to station, we ask them to put the monitor back on and take another manual reading on the way back to station. After that, blood pressure measures will continue to be taken automatically at 30-min intervals.

If they are not a firefighter, we will instruct how to download a mobile app which we will use to randomly page them 1 or 2 times over the 12-hour period. They will also push the monitor's button to force an automatic blood pressure reading.

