## RISKS

The possible **risks**, exactly as described in the consent form, include the following:

*Loss of Confidentiality:* Once others know that you are participating in the study, you may lose some confidentiality. Fire crews work in close quarters and some spend time living together in the fire house, so confidentiality may be lost by your presence at the testing appointments. We will reduce this risk because your name will not be on any documents and your personal data will not be shown to anyone during the test sessions.

*Depression, Anxiety, and Stress Scales (DASS-21):* The risk associated with completing this short 21-item survey is that you may feel uncomfortable while answering the questions. If you feel this and your symptoms are severe, we will work with you to refer you to a proper clinician who is part of your health network.

*Blood glucose, cholesterol, and blood draw:* These measurements will involve a finger prick and a needle stick. The risks associated are slight discomfort in the site. These are routine and conventional procedures used to measure blood levels of metabolites. Minor risks include a small amount of bleeding under the skin (bruising), but this has been reported in <10% of the cases, dizziness, and a very small risk of infection (1 in 1000). The risk of infection will be reduced by proper cleaning and antiseptic techniques by the technician.

*Blood vessel studies:* The blood vessel ultrasound studies may include discomfort in the arm and leg when the cuff squeezes to take a measurement. This feeling could be similar to what is felt when a foot or leg falls asleep after sitting in certain positions. This is not a risk to your health, but it is a discomfort. To help with this risk, we recommend that you stay very still and as the blood flows back to the arm and the feeling will go away.

*Fitness testing/training:* The risk of any exercise is injury to muscles, joints, ligaments, and tendons. It has been found that in 1 out of every 70,000 exercise tests, a person could die from heart problems. In medical terms, doctors call this a rare event. Because you are otherwise healthy with no known risk factors, the risks of a medical problem are even lower. You are aware that if any exercise makes you uncomfortable, you should notify us immediately.

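### The ambulatory monitor instructions make no exception for a participant who is driving, and the risk list has no item for the monitor

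*Combined protocol and SAP*

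**What the plan says.** All of the monitor instructions stand under Blood Pressure Monitoring appointment.

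- **Everyone wearing the monitor:** "when the pager goes off, they will push the monitor's button to force an automatic blood pressure reading".
- **Firefighters only, before the call:** "If they are a firefighter, we also ask that they remove the monitor device right before donning fire gear". The monitor then travels with them on the apparatus.
- **Firefighters only, after the call, once aboard for the return:** "we ask them to put the monitor back on and take another manual reading on the way back to station".
- **Civilians only:** the team uses a mobile app to "randomly page them 1 or 2 times over the 12-hour period". At a page, "They will also push the monitor's button to force an automatic blood pressure reading". Civilians are not asked to remove or refit the cuff.

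Post-Intervention Testing Visits repeats all the tests, so the monitor is worn twice.

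The RISKS section introduces its list with "exactly as described in the consent form, include the following". The items are loss of confidentiality, the DASS-21, finger prick and blood draw, blood vessel studies, fitness testing and training, and the diet. The only cuff discomfort described belongs to the laboratory blood vessel studies.

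**The concern.** The return instruction fixes both an action (refit the cuff and take a manual reading) and a time (during the trip, not after arrival). A returning apparatus has a driver. If that person is a participant, the instruction as written applies to them too. A random page to a civilian can likewise arrive while that person is driving, and the instruction is to press the button.

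At stake is the safety of the participant, the crew and other road users, and whether the consent form describes a procedure that lasts 12 hours and is done twice. There is a smaller data point. If a person who is driving sensibly waits before pressing the button, the plan has no way to mark that reading as delayed, and it would be treated as an immediate response to the alarm.

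**Working it through.** The plan states no figure on this point, so there is none to reproduce. The check compares the instructions with the risk list, counts occasions from the stated schedule, and asks which readings bear on the aims.

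**1. Instructions against exceptions**

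| Participant | Action | When | Exception for driving |
|---|---|---|---|
| Firefighter | Press button | When the pager sounds | None stated |
| Firefighter | Refit cuff, take manual reading | During the return trip | None stated |
| Civilian | Press button | At a random app page | None stated |

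No section in the available text mentions driving.

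**2. Procedures against risks**

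Six items are listed under RISKS. None concerns the ambulatory monitor, the response to a page, or use of the monitor in a vehicle.

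**3. Count from the schedule**

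- Automatic readings: 12 h ÷ 0.5 h = about 24 per session. These need no action by the wearer.
- Civilian pages: 1 to 2 per session × 2 sessions (pre and post) = 2 to 4 per civilian.
- Firefighter return readings: one per call. The number of calls is not stated.

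**4. How often a driver would be reached**

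This cannot be calculated. The documents give neither time spent driving, nor crew size, nor the number of enrolled firefighters who drive the apparatus. The following only illustrates what assumptions would imply.

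- Assume a civilian drives 1 to 2 of the 12 hours, with pages uniform in time and independent. One page reaches a driver with probability 1/12 = 8.3% to 2/12 = 16.7%. With two pages, at least one does so with probability 1 − (11/12)² = 16.0% to 1 − (10/12)² = 30.6%.
- Assume a crew of 3 to 4, all enrolled and wearing the monitor. The driver then accounts for 1/4 = 25% to 1/3 = 33% of return readings. If drivers are not enrolled, the share is zero.

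These percentages describe possible exposure, not harm, and the conclusion does not depend on them.

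**5. Which readings matter to the aims**

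Specific Aims and DATA concern the surge at the pager alarm. For a firefighter that reading comes from the button press at the alarm, before the monitor is removed. The return-trip reading comes later, and no post-call endpoint is named. A poor or missing return reading is therefore not shown to affect any aim. Only a page that arrives while someone is driving could touch the surge data, through a missing reading or a delayed one.

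**The case against.** The strongest reply is that the plan never tells anyone to use the monitor while driving. A reader might infer that the rules apply in full to everyone and direct people to handle a cuff and button at the wheel. The documents do not support that. Refitting is a firefighter instruction, civilians only press a button, and driving is not mentioned at all. The defect is a missing exception.

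A reader might also infer that the return-trip readings corrupt the surge outcome. They are not alarm readings, so this is not shown. The plan does say that the monitor fails to record during movement, but it says so to explain removal before gear is worn. Extending it to seated driving is an inference, and a failed recording would be a missing value rather than a false one.

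The set-up visit may include a spoken safety instruction. The consent form itself and one part of the document, between Post-Intervention Testing Visits and DATA, were not available to check. A spoken warning can be neither confirmed nor ruled out. The risk list, however, is available and is said to match the consent form.

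Finally, the plan calls the method effective and says that prior cohorts used it. It reports nothing about safety or about drivers. Elsewhere, under Fitness Testing Appointment, the plan does adapt a procedure to protect the community that the crew serves, so a written exception here would be in keeping with its own approach.

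What stands of the objection is that the frequency is unknown and that nothing shown invalidates the aims or the analysis. What does not fall is the unqualified timing of the return reading, the unqualified response to a page, and the absence of the monitor from the risk list.

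**Conclusion.** The concern holds as a gap in safety instructions and risk disclosure. The absence of a driving exception and of a monitor item among the six listed risks can be read directly from the text and needs no assumption. The hazard follows only if an apparatus driver takes part, or a page arrives while a participant is driving, and the person follows the instruction literally. Its frequency cannot be derived from the documents. For the surge outcome, the only route is a page answered late or missed because of driving; no effect is shown for the return-trip reading.

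This is a should-fix item and a cheap improvement. It is not a flaw that undermines the analysis.

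**What to change.** 1. Under Blood Pressure Monitoring appointment, state that nobody fits, handles or triggers the monitor while driving. The apparatus driver refits it and takes the return reading once parked. A civilian paged while driving does not respond, notes the page afterwards, and is paged again later where feasible.
2. Record and flag delayed button presses, and state under DATA that they are not analysed as immediate pager-alarm readings.
3. Add the ambulatory monitor, including its use in vehicles, to the RISKS list and to the consent form, so that the two still match.

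The cost is a few sentences in the protocol and consent form, a small change to the paging procedure and its log, and a few delayed or missing readings.
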